#### 12.2.2. Patient Disposition

A detailed description of patient disposition will be provided. It will include:

- total number of patients enrolled; and
- total number of patients treated (safety population).

A detailed summary of reasons for patient discontinuation from treatment will be provided. A summary of all identified major protocol violations will be provided.

### **12.2.3. Patient Characteristics**

A detailed description of patient characteristics at baseline will be provided, including:

- patient demographics;
- baseline disease characteristics; and
- medical history.

### **12.2.4. Concomitant Therapy**

Concomitant medications will be summarized for the safety population.

#### **12.2.4.1. Postdiscontinuation Therapy**

The numbers and percentages of patients reporting postdiscontinuation therapies will be provided overall, by type of therapy (surgery, radiotherapy, or systemic therapy), and by drug name.

### **12.2.5. Treatment Compliance**

The number of dose omissions, reductions, and delays, the number of cycles received, and dose intensity will be summarized for all treated patients.

Compliance information for abemaciclib will be collected through capsule counts at each cycle/visit. The estimate of percent compliance will be given by:

$$\text{Percent Compliance} = \frac{\text{Actual cumulative dose taken}}{\text{Expected cumulative dose to be taken}} \times 100$$

The actual cumulative dose taken will be determined based on counting the number of capsules returned at each visit and subtracting that number from the number of capsules dispensed. The expected cumulative dose to be taken will be determined based on the assigned dose and taking into account any dose reductions or suspensions.

### **12.2.6. Primary Outcome and Methodology**

Please refer to Section [12.1](#) for details of the primary analysis.

#### **12.2.6.1. Analyses of Efficacy**

In addition to the analyses described in Section [12.1](#), this section provides additional details of planned efficacy analyses. For time-to-event variables, the Kaplan-Meier method will be used to estimate parameters (for example, medians, quartiles, 1-year event rates). See also the SAP for this study for additional details.

[Table JFCU.12.1](#) provides definitions of key efficacy statistics used for this study. Exact 95% confidence intervals will be calculated for ORR and DCR.

**Table JFCU.12.1. Definitions of Key Efficacy Statistics**

Efficacy Statistic	Definition
Objective Response Rate (ORR)	The denominator of ORR includes each patient enrolled who receives any amount of study drug (necitumumab or abemaciclib), who has a complete radiographic assessment at baseline, and who has at least 1 complete radiographic assessment postbaseline. The numerator includes those patients counted in the denominator with a best overall tumor response of PR or CR.
Disease Control Rate (DCR)	Using the same denominator as for ORR, the numerator of the DCR includes those patients counted in the denominator with a best tumor response of SD, PR, or CR.
Median (OS, PFS)	Estimated using Kaplan-Meier method of estimation

Abbreviations: CR = complete response; DCR = disease control rate; ORR = objective response rate; OS = overall survival; PFS = progression-free survival; PR = partial response; SD = stable disease.

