### 12.2. Statistical and Analytical Plans

#### 12.2.1. General Considerations

The primary analysis will be as described in Section 12.1.

All summary analyses, including efficacy and safety analyses, will be performed for all patients enrolled in the study who receive any amount of study drug (necitumumab and abemaciclib).

Minor changes or clarifications to any statistical analyses described in this protocol may be presented in the final statistical analysis plan (SAP) for this study.

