5.2. General Considerations

The following populations will be defined for this study:

- **All enrolled population:** anyone who signed the informed consent will be included in this population.
- **Safety population:** all patients who have received any amount of study drug [necitumumab, and/or abemaciclib]
- **Evaluable population:** all patients who have received at least 1 dose each of necitumumab and abemaciclib and have had a complete radiographic assessment at baseline

Unless otherwise specified, for continuous variables, summary statistics will include number of patients, mean, median, standard deviation, minimum, and maximum. Categorical variables will be summarized using frequency and percentages.

- **Age (years):** $(\text{Informed Consent Date} - \text{Date of Birth} + 1)/365.25$, if only year of birth is collected, see Section 5.3 for date imputation.
- **Missing Data:** All analyses and descriptive summaries will be based on the observed data. Unless otherwise specified, missing data will not be imputed or “carried forward.”
- **Baseline Measurement:** Unless otherwise specified, the last nonmissing measurement prior to the first dose of study drug will serve as the baseline measurement.
- **Study Day:** Study day is calculated as assessment date – first dose date + 1 day if the assessment is done on or after the first dose day. If the assessment is done prior to the first dose day, study day will be calculated as assessment date – first dose date. Date of first dose is defined as study day 1.
- **Duration:** Duration is calculated as:
 - Duration (days): $(\text{End Date} - \text{Start Date} + 1)$
 - Duration (weeks): $(\text{End Date} - \text{Start Date} + 1)/7$
 - Duration (months): $(\text{End Date} - \text{Start Date} + 1)/30.4375$ (Days in months = $(1/12) \times \text{average number of days in a year.}$)
 - Duration (years): $(\text{End Date} - \text{Start Date} + 1)/365.25$ (Average days in a year = 365.25, reflecting the Julian Year of 3 years with 365 days each and one leap year of 366 days.)
- **Time-to-event:** The event or censoring time (days) is calculated as:
Date of event/censoring – Date of first dose of study drug + 1

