5.6. Efficacy Analyses

Efficacy analyses will be performed for the evaluable population. For all time-to-event variables (OS and PFS), the Kaplan-Meier product limit method will be used to estimate the survival curve as well as survival rates at various time points (3-month, 6-month, and 1-year). A 2-sided, 95% confidence interval (CI) for median PFS, median OS, and survival rate at time point will be computed by the Brookmeyer and Crowley method.

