5.6.2. Secondary Efficacy Endpoints

5.6.2.1. Overall Response Rate

The denominator of overall response rate (ORR) includes all evaluable patients and the numerator includes those patients counted in the denominator with a best overall tumor response of PR or CR per RECIST 1.1. Confirmation of objective response is required for this trial. To be assigned a best overall response status of PR or CR, changes in tumor measurements must be confirmed by repeat assessments that should be performed no less than 4 weeks after the criteria for response are first met. In this circumstance, the best overall response can be interpreted as in [Table JFCU.5.2](#). In the case of SD, measurements must have met the SD criteria at least once after first dose at a minimum interval of 6 weeks. Patients' responses after objective progression or start of new anticancer therapy are excluded from the determination of best response. The ORR and its exact 95% CIs will be estimated.

Table JFCU.5.2. Best Overall Response when Confirmation of CR and PR Required

Overall Response First Time point	Overall Response Subsequent Time point	BEST Overall Response
CR	CR	CR
CR	PR	SD, PD, or PR ^a
CR	SD	SD provided minimum criteria for SD duration are met. Otherwise, PD
CR	PD	SD provided minimum criteria for SD duration are met. Otherwise, PD
CR	NE	SD provided minimum criteria for SD duration are met. Otherwise, NE
PR	CR	PR
PR	PR	PR
PR	SD	SD
PR	PD	SD provided minimum criteria for SD duration are met. Otherwise, PD
PR	NE	SD provided minimum criteria for SD duration are met. Otherwise, NE
NE	NE	NE

Abbreviations: CR = complete response; NE = inevaluable; PD = progressive disease; PR = partial response; SD = stable disease.

^a If a CR is truly met at first time point, then any disease seen at a subsequent time point, even disease meeting PR criteria relative to baseline, makes the disease PD at that point (since disease must have reappeared after CR). Best response would depend on whether minimum duration for SD was met. However, sometimes 'CR' may be claimed when subsequent scans suggest small lesions were likely still present and in fact the patient had PR, not CR at the first time point. Under these circumstances, the original CR should be changed to PR and the best response is PR.

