5.6.2.2. Disease Control Rate

Disease control rate (DCR) will be analyzed, with the same denominator as defined in ORR. Among patients counted in the denominator, the numerator counts those with a confirmed best tumor response of SD, PR, or CR per RECIST 1.1. The DCR and its exact 95% CI will be estimated.

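### The protocol and SAP define different denominators for ORR and DCR; among patients given both drugs, the protocol's post-baseline scan condition raises both rates

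*Protocol*

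**What the plan says.** **Protocol, Table JFCU.12.1 (section 12.2.6.1).** The ORR denominator has three conditions:
- treatment: "The denominator of ORR includes each patient enrolled who receives any amount of study drug (necitumumab or abemaciclib";
- a complete baseline assessment;
- follow-up: a patient "who has at least 1 complete radiographic assessment postbaseline".

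DCR is built "Using the same denominator as for ORR".

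**SAP.** Section 5.6 states: "Efficacy analyses will be performed for the evaluable population". Section 5.6.2.1 states: "The denominator of overall response rate (ORR) includes all evaluable patients". Section 5.2 defines the evaluable population as "all patients who have received at least 1 dose each of necitumumab and abemaciclib and have had a complete radiographic assessment at baseline". Section 5.6.2.2 analyses DCR "with the same denominator as defined in ORR".

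**Which governs.** Protocol 12.2.1 says in general terms: "All summary analyses, including efficacy and safety analyses, will be performed for all patients enrolled in the study who receive any amount of study drug". It also lets the SAP present minor changes or clarifications. Protocol 12.2.6.1 refers to the SAP for further detail. The SAP's revision history mentions interim efficacy analyses and new output templates, but no denominator change. Neither document says which definition prevails for ORR and DCR.

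**The concern.** The two definitions differ in two ways. The protocol adds a post-baseline scan condition that the SAP lacks, and it accepts either drug where the SAP requires both.

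The scan condition matters more because it selects on something related to outcome. The first scheduled scan is 6 weeks after first dose (Protocol 10.1.1). Patients with no complete scan after baseline will include those who die early, start new anticancer therapy early, withdraw from the study, or have only incomplete scans. An evaluable patient who dies before the first scan is an event for PFS (Protocol 10.1.3, SAP 5.6.1). Under the protocol table that same patient disappears from ORR and DCR.

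ORR is a secondary objective in both parts and DCR in Part B. The trial is open-label and single-arm, and SAP 5.10 allows an interim look at ORR in nonsquamous patients to help plan future trials. The denominator should be the same in both documents before rates are read.

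**Working it through.** **1. The plan's own figure.** No expected value or precision is stated for ORR or DCR. The only design figure to reproduce is the Part B test: 50 evaluable patients, reject if at least 60% (30 patients) are progression-free at 3 months. Exact binomial:
- P(X ≥ 30 | n = 50, p = 0.50) = 0.101; stated 10%.
- P(X ≥ 30 | n = 50, p = 0.65) = 0.814; stated 81%.

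Both agree after rounding. Neither uses the ORR/DCR denominator.

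**2. Direction of the scan condition.** CR and PR need post-baseline measurements. SD needs a qualifying measurement at least 6 weeks after first dose (SAP 5.6.2.1). A patient with no post-baseline scan can be none of these. Dropping the patient leaves the numerator x unchanged and reduces the denominator:
- SAP rate = x/50
- Protocol rate = x/(50-m)
- Ratio = 50/(50-m)

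Here 50 is the planned Part B evaluable number (Protocol 12.1, SAP 5.1). m is the number of those patients with no post-baseline scan.

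**3. Size.** The values of m, the 25 controlled and the 5 responders are all assumptions; the documents give none of them.

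| m | Factor | DCR, SAP 25/50 | DCR, protocol | ORR, SAP 5/50 | ORR, protocol |
|---|---|---|---|---|---|
| 2 | 50/48 = 1.04 | 50% | 25/48 = 52.1% | 10% | 5/48 = 10.4% |
| 5 | 50/45 = 1.11 | 50% | 25/45 = 55.6% | 10% | 5/45 = 11.1% |
| 7 | 50/43 = 1.16 | 50% | 25/43 = 58.1% | 10% | 5/43 = 11.6% |
| 10 | 50/40 = 1.25 | 50% | 25/40 = 62.5% | 10% | 5/40 = 12.5% |

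For scale, the exact 95% intervals at m = 5 are:
- DCR: 35.5 to 64.5% (SAP) against 40.0 to 70.4% (protocol);
- ORR: 3.3 to 21.8% (SAP) against 3.7 to 24.1% (protocol).

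**4. The offset from the treatment condition.** Let k be patients who received only one drug, have complete baseline and post-baseline scans, and are neither responders nor controlled. They enter only the protocol denominator, so the ratio becomes 50/(50-m+k). With m = 5 and k = 1 it is 50/46 = 1.09; with k = m it is 1. The documents do not give k. Protocol 9.1 has abemaciclib taken within 10 minutes of the start of the infusion, which suggests that k would be small.

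**5. Incomplete scans.** The formula is exact for patients with no post-baseline scan at all. The protocol's condition also drops a patient whose only post-baseline scans were incomplete. Under Attachment 6, Table 1, such a patient could still be PR or SD if only nontarget lesions were missed, or PD from a new lesion. Dropping a PR or SD patient removes a numerator count too, so that case does not follow the formula.

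**6. How the cited single-agent rates were built.** The DCRs in Protocol 5.2 and 5.3 divide by all patients:
- abemaciclib NSCLC cohort: (2+26)/57 = 49%;
- necitumumab Western study: (1+8)/29 = 31% and (1+8)/31 = 29%;
- necitumumab Japanese study: 10/15 = 66.7%.

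Table JFCU.12.1 would put this trial's DCR on a more favourable basis than those figures.

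**The case against.** The strongest reply is that the SAP already settles this in practice. It gives one denominator, with no option and no post-baseline condition. Its best-response table includes an inevaluable outcome, and only CR/PR or CR/PR/SD enter the numerators. Unscanned patients therefore already count as failures. The protocol sends the reader to the SAP. The endpoints are descriptive, and Protocol 8.2 calls the study hypothesis generating only. In the illustration ORR moves by at most 2.5 points, well inside its interval.

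Most of this stands. It locates the error in the protocol table and limits the consequence. It does not remove the conflict: the protocol refers to the SAP for additional detail rather than a replacement definition, and no rule of precedence is given.

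Several stronger readings are tempting but not supported:
- **That Protocol 12.2.1 sets a third competing denominator.** It is a general statement, and the table is the specific definition. The clause needs tidying, but it is not a rival ORR definition.
- **That everyone who stops treatment before week 6 is dropped.** Protocol 10.1.2 continues scans after discontinuation without progression, until progression, new therapy or study completion. A complete scan showing progression keeps the patient in.
- **That the protocol wording always inflates.** It does so among patients given both drugs who have no post-baseline scan. One-drug nonresponders pull the other way, and with m = 0 or an empty numerator the scan condition changes nothing.
- **That the SAP has breached the limit on minor changes.** Protocol 12.2.1 does not define minor, so this would be opinion.

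**Conclusion.** The point holds as a conflict between the documents, with the protocol table wrong as written. Among patients who received both drugs, its scan condition removes people who cannot enter the numerator and raises ORR and DCR by 50/(50-m): 4% in relative terms at m = 2, 11% at m = 5, 16% at m = 7 and 25% at m = 10. In absolute terms, with the assumed numerators, DCR rises by about 2 to 12.5 points and ORR by 0.4 to 2.5 points. These sizes rest on assumed m and assumed numerators, take no account of one-drug patients, and treat m as patients with no post-baseline scan at all.

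A reader might infer that the reported rates are open to free choice, or that the main conclusion is at risk. Neither follows. The SAP specifies a single, more conservative denominator, so inflation arises only if the protocol table is followed instead. The primary 3-month PFS test, its sample size, alpha and power do not depend on this definition. It should be corrected because the affected endpoints are named objectives and the correction is easy.

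**What to change.** 1. **Table JFCU.12.1.** Replace the ORR denominator with the SAP evaluable population: at least one dose of each drug and a complete baseline scan, with no post-baseline scan condition. DCR follows automatically.
2. **Explicit rule.** State that patients without a post-baseline scan count as nonresponders and as not controlled, and report how many there are.
3. **Protocol 12.2.1.** Change only the efficacy clause so that it refers to this population. Leave the safety population as all treated patients. Moving the whole sentence to the evaluable population would remove one-drug patients, and those without a complete baseline scan, from the safety summaries, contrary to the safety population in SAP 5.2 and Protocol 12.2.2.

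The cost is a wording amendment. No new data, patients or analyses are needed beyond one reported count. The downside is slightly less favourable rates than the protocol wording would give.

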### **12.2.7. Pharmacokinetic and Immunogenicity Analyses**

PK analyses will be conducted on patients who have received at least 1 dose of either study drug and have had samples collected.

PK parameter estimates will be computed for abemaciclib and its metabolites. The abemaciclib PK parameters will be computed by standard noncompartmental methods of analysis using WinNonlin Professional Edition on a computer that meets or exceeds the minimum requirements for this program.

The primary parameters for analysis will be maximum concentration and area under the concentration-time curve ( $AUC_{0-t_{last}}$ ,  $AUC_{0-\infty}$ ). Other noncompartmental parameters, such as time of half-life, apparent clearance (CL/F), and apparent volume of distribution (V/F) may be reported.

Summary statistics of necitumumab PK data will be presented graphically as well as in tabulated form. Additional exploratory analyses will be performed if warranted by data, and other validated PK software programs (for example, NONMEM) may be used if appropriate and approved by Global Pharmacokinetic management. The version of any software used for the analysis will be documented, and the program will meet the Lilly requirements of software validation.

Serum concentrations of necitumumab and plasma concentrations of abemaciclib and metabolites at each sampling time point will be summarized using descriptive statistics. Immunogenicity (anti-necitumumab antibody) incidence will be tabulated, and correlation to necitumumab drug level, activity, and safety will be assessed, as appropriate. Additional exploratory analyses will be performed if warranted by data, using validated PK software programs (for example, NONMEM) and if appropriate and approved by Global Pharmacokinetic management. The version of any software used for the analysis will be documented and the program will meet Lilly requirements for software validation.

Interim analysis may be conducted to facilitate exploratory analyses of PK, safety, and immunogenicity through PK/pharmacodynamic modeling. Interim data may also be pooled with final and interim data from other clinical studies of necitumumab or abemaciclib to facilitate

meta-analysis using non-linear mixed effects modeling. Since the study is unblinded, study objectives will not be compromised by the interim access to data.

### **12.2.8. Translational Research Analyses**

Biomarker results will be summarized and correlated with clinical outcomes.

### **12.2.9. Safety Analyses**

All safety summaries and analyses will be based upon the Safety Population as defined in Section [12.2.2](#).

Overall exposure to study drugs, the numbers of patients completing each cycle, and the dose intensity will be summarized using descriptive statistics. The number of patients with any dose adjustment will be presented for entire treatment period. The number of patients with dose reductions, dose delays, or dose omissions will also be summarized, as will the reasons for dose adjustments.

An overall summary of AEs will be provided for AEs deemed by the investigator to be possibly related to study treatment, and repeated for events regardless of study drug causality.

A treatment-emergent adverse event (TEAE) is defined as an event that first occurred or worsened between the first dose of study treatment and 30 days after the last dose of study treatment and related SAEs reported beyond 30 days after the last dose of study treatment.

The number of patients who experienced a TEAE, SAE, AE related to study treatment, died, or discontinued from the study therapy due to an AE will be summarized.

Common Terminology Criteria for Adverse Events v 4.0 will be used to report AEs by CTCAE terms.

Laboratory and non-laboratory CTCAEs will be summarized by CTCAE term and maximum CTCAE grade, including the total for maximum Grade 3 and above. These summaries will be provided for events deemed by the investigator to be possibly related to study treatment and repeated for events regardless of causality.

MedDRA Version 17.0 (or higher) will be used when reporting AEs by MedDRA terms.

Treatment-emergent adverse events will be summarized by System Organ Class (SOC) and by decreasing frequency of Preferred Term (PT) within SOC.

Reasons for death will be summarized separately for on-therapy and within 30 days of last dose of study drug. Serious adverse events will be summarized by PT.

Hospitalizations and transfusions during the study treatment period or during the 30-day short-term follow-up period will be summarized.

**12.2.10. Interim Analyses**

A safety interim analysis will be performed after the first 15 evaluable patients in the Part B portion of the trial have completed 2 cycles of study treatment (or otherwise discontinued study treatment).

The safety interim analysis will be conducted to permit evaluation of safety data by Lilly.

The results from the safety interim analysis will be examined by an internal assessment committee, which will be established prior to enrollment of the first patient in the trial. The internal assessment committee will consist of a Lilly medical director, a Lilly CRP/clinical research scientist, a PK scientist, and a statistician and will make recommendations about the trial. Enrollment will continue while the safety interim analysis is being performed. The safety interim analysis results (including all tables, figures, and listings) will not be disseminated outside of the assessment committee, unless emerging safety outcomes warrant such a disclosure. In case a disclosure is warranted, the outcome of the safety interim analysis will be documented and a written letter will be submitted to the ERB(s) and the investigators for documentation purposes.

Interim analyses for efficacy may be performed as needed to aid in the planning of future trials. There is no plan to stop the study for positive efficacy. The type-1 error for final primary analysis will not be affected and hence is not adjusted.

Patients with squamous and nonsquamous NSCLC who received the recommended abemaciclib dose for Part B in Part A will be taken into account for the interim analyses.

